**Table 16-6 GFR by age for initiation/up-titration and exclusion criteria**

Age range*	$\geq 30\%$ mean GFR for age (mL/min/1.73m  )**	< 30% mean GFR for age (mL/min/1.73m  )***
12 months to < 19 months (1 year, 7 months)	$\geq 31$	< 31
19 months to < 18 years	$\geq 38$	< 38
$\geq 18$ years	$\geq 30$	< 30

\* Age rounded to nearest whole number

\*\* Initiation/up-titration criteria

\*\*\* Exclusion criteria

Source: ([Peters and Gordon 1999](#))

## 16.4 Appendix 4: Guidelines for the management of renal dysfunction

### General principles:

Glomerular filtration rate in HF patients depends on intrinsic renal function and on a balance between afferent and efferent glomerular arterial tonicity. This tonicity is partly regulated by a stimulation of angiotensin II and could be affected by either study medication. Moreover, renal dysfunction may develop or may deteriorate in some patients after study drug administration. These recommendations have been developed to guide the investigators in managing patients with renal dysfunction after OLE enrollment and the first OL dose of LCZ696.

Two types of response to serum creatinine increase are described:

#### Surveillance situation

If, at any time after OLE enrollment and the first open-label dose of LCZ696, eGFR%\* decreases by  $\geq 50\%$  from baseline in the PANORAMA-HF core study (i.e. Visit 301 for Part 2), the investigator will check for potentially reversible causes of renal dysfunction such as:

- non-steroidal anti-inflammatory drug intake, antibiotics, or other treatments known to cause creatininemia
- volume decrease, including that resulting from excessive dosing of diuretics
- urinary infection
- urinary tract obstruction
- study medication

#### Action situation

If a patient eGFR\* decreases by  $\geq 50\%$  from baseline of the core study (i.e. Visit 301 for Part 2) (or if serum creatinine concentration rises above 3 mg/dL (265  $\mu$ mol/L), the investigator will check for potentially reversible causes of renal dysfunction (see above). If the investigator judges that study medication has to be stopped, he/she will have to contact the Novartis medical monitor or his/her designee. Thereafter, serum creatinine assessments will have to be repeated at least each week until levels return to acceptable values. If study medication was stopped, every effort will be done to restart it again, according to clinical conditions.

\*eGFR is calculated using a modified Schwartz formula for subjects  $<18$  years.

For subjects  $\geq 18$  years, an adult formula for eGFR will be utilized (Reference: Novartis Nephrology Guidance document)

[figure not shown]
## 16.5 Appendix 5: American heart association (AHA) pediatric advanced life support (PALS) guidelines

**Table 16-7 5th percentile systolic blood pressure (SBP) table**

Age	SBP percentile	SBP (mmHg)
1 month to < 1 year	5 th	70
1 year	5 th	72
2 years	5 th	74
3 years	5 th	76
4 years	5 th	78
5 years	5 th	80
6 years	5 th	82
7 years	5 th	84
8 years	5 th	86
9 years	5 th	88
10 years	5 th	90
11 years	5 th	90
12 years	5 th	90
13 years	5 th	90
14 years	5 th	90
15 years	5 th	90
16 years	5 th	90
17 years	5 th	90

\* AHA PALS guidelines 2010 ([Kleinman et al 2010](#)) are widely used criteria for hypotension in acute HF patients. The formula (for 1 year and older: 70 mmHg + 2 x Age, up to age 10) is understood to provide the 5th SBP percentile up to 10 years. For children 1 month to < 1 year and >10 years, the AHA PALS guidelines 2010 5th percentile is set at 70 mmHg and 90 mmHg respectively. NOTE:

This formula approximates the population-based 5th percentile BP data; however, the margin of error increases with increasing age, with the PALS formula value generally providing a lower value.

**16.6 Appendix 6: Guidelines for the management of blood pressure**

1. Investigator should monitor blood pressure closely.
2. If symptomatic hypotension occurs:
  - Correct any treatable cause, e.g. hypovolemia
  - If hypotension persists, any antihypertensive drug and non-disease-modifying drugs, such as diuretics, calcium channel blockers (CCBs), nitrates, and  $\alpha$ -blockers, should be down-titrated or stopped first before down-titration of the study drug is considered
  - If hypotension persists, the study drug should be down titrated or even temporarily withdrawn.

## 16.7 Appendix 7: Treatment guidelines for elevated potassium and hyperkalemia (serum potassium $\geq 5.3$ mmol/L)

### General principles

Elevation of potassium levels on a non-hemolyzed specimen above the predefined values should be repeated and confirmed before any action, if appropriate based on investigator's medical judgment.

For assessment of potassium, no blood sample should be drawn by finger or heel stick. Also note that pH can affect potassium values, and that abnormal potassium values should include assessment of pH. Each 0.1 increase in pH represents a 0.6 mEq/L change in the opposite direction of the pH change.

Patients with elevated potassium value will be managed according to the corrective actions outlined below. Hyperkalemia should be followed until resolution.

### Corrective action for management of elevated potassium and hyperkalemia

#### Serum potassium $> 5.2$ and $\leq 5.4$ mmol/L

Confirm potassium concentration in a non-hemolyzed sample.

Reinforce low potassium diet and restriction of food/drinks with high potassium content (e.g. orange juice, melon, bananas, low-salt substitutes etc.).

Review medical regimen (including dietary supplements and over-the-counter medications) for agents known to cause hyperkalemia. Consider reduction in dose or discontinuation of these agents:

- Aldosterone antagonists (if they are believed to be the most likely cause of hyperkalemia)
- Potassium-sparing diuretics (e.g. amiloride and triamterene) including in combination products with thiazide or loop diuretics
- Potassium supplements, e.g. potassium chloride
- Salt substitutes
- Non-steroidal anti-inflammatory drugs (NSAIDs)
- Cyclo-oxygenase-2 (COX-2) inhibitors
- Trimethoprim and trimethoprim-containing combination products, such as Bactrim® and Septra® (trimethoprim/sulfamethoxazole fixed combination)
- Herbal Supplements: For example, Noni juice, alfalfa (*Medicago sativa*), dandelion (*Taraxacum officinale*), horsetail (*Equisetum arvense*), nettle (*Urtica dioica*), milkweed, lily of the valley, Siberian ginseng, hawthorn berries.

Repeat serum potassium measurement within 3 to 5 days. If serum potassium remains  $> 5.2$  and  $\leq 5.4$  mmol/L, regularly monitor serum potassium levels to ensure stability suggested once monthly.

Consider down-titration of study medication, according to investigator's medical judgment.

**Serum potassium > 5.4 and < 6.0 mmol/L**

Confirm potassium concentration in a non-hemolyzed sample.

Consider down-titration or temporarily discontinue study drug according to investigator medical judgment.

Apply all measures outlined for serum potassium > 5.2 and  $\leq$  5.4 mmol/L.

Repeat serum potassium measurement after 2-3 days.

- If serum potassium < 5.4 mmol/L, consider resumption of study drug at lower dose with repeat potassium within 5 days.

**Serum potassium  $\geq$  6.0 mmol/L**

[figure not shown]
Confirm potassium concentration in a non-hemolyzed sample.

Urgently evaluate patient and treat hyperkalemia as clinically indicated.

Apply all measures outlined for serum potassium > 5.4 and < 6.0 mmol/L.

Study drug should be immediately interrupted or discontinued if the serum potassium is greater than or equal to 6.0 mmol/L.

No resumption of study drug without individualized case discussion with and permission from Novartis medical monitor or his/her designee.

## 16.8 Appendix 8: Reference table – blood volume by weight

**Table 16-8 Reference table – blood collection volumes by body weight (kg)**

2.5% and 5% Blood volume table by weight (up to 35 kg) 			
Body Weight (Kg)	Total blood volume of the patient (mL)	Maximum allowable volume (mL) in one blood draw (= 2.5% of total blood volume of the patient)	Total maximum volume (mL) drawn in a 28-day period (= 5% of total blood volume of the patient)
2.5	200	5	10
3	240	6	12
3.5	280	7	14
4	320	8	16
4.5	360	9	18
5	400	10	20
5.5	440	11	22
6	480	12	24
6.5	520	13	26
7	560	14	28
7.5	600	15	30
8	640	16	32
8.5	680	17	34
9	720	18	36
9.5	760	19	38
10	800	20	40
10.5	840	21	42
11	880	22	44
11.5	920	23	46
12	960	24	48
12.5	1000	25	50
13	1040	26	52
13.5	1080	27	54
14	1120	28	56
14.5	1160	29	58
15	1200	30	60
15.5	1240	31	62
16	1280	32	64
16.5	1320	33	66
17	1360	34	68
17.5	1400	35	70
18	1440	36	72
18.5	1480	37	74
19	1520	38	76
19.5	1560	39	78

**2.5% and 5% Blood volume table by weight (up to 35 kg)**

Body Weight (Kg)	Total blood volume of the patient (mL)	Maximum allowable volume (mL) in one blood draw (= 2.5% of total blood volume of the patient)	Total maximum volume (mL) drawn in a 28-day period (= 5% of total blood volume of the patient)
20	1600	40	80
20.5	1640	41	82
21	1680	42	84
21.5	1720	43	86
22	1760	44	88
22.5	1800	45	90
23	1840	46	92
23.5	1880	47	94
24	1920	48	96
24.5	1960	49	98
25	2000	50	100
25.5	2040	51	102
26	2080	52	104
26.5	2120	53	106
27	2160	54	108
27.5	2200	55	110
28	2240	56	112
28.5	2280	57	114
29	2320	58	116
29.5	2360	59	118
30	2400	60	120
30.5	2440	61	122
31	2480	62	124
31.5	2520	63	126
32	2560	64	128
32.5	2600	65	130
33	2640	66	132
33.5	2680	67	134
34	2720	68	136
34.5	2760	69	138
35	2800	70	140

Blood volume drawn for the purpose of this study is limited to a maximum of 2.5% of the circulating blood volume per sampling session and to a maximum of 5% over a 4-week period ([Howie 2011](#)). Investigators may further limit the volume of blood withdrawn based on local institutional guidelines and if the clinical condition of the patient may be adversely affected by removal of the blood volumes stated above. Details about blood volume requirement for safety samples are provide in the laboratory manual.

 For body weights >35 kg, use the following formulas to calculate 2.5% and 5% of total blood volume:  
**2.5% of total blood volume = body weight (in kg to the closest 0.5 kg) X 2**

**2.5% and 5% Blood volume table by weight (up to 35 kg)**

Body Weight (Kg)	Total blood volume of the patient (mL)	Maximum allowable volume (mL) in one blood draw (= 2.5% of total blood volume of the patient)	Total maximum volume (mL) drawn in a 28-day period (= 5% of total blood volume of the patient)
-------------------------	---	--	---

**5% of total blood volume = body weight (in kg to the closest 0.5 kg) X 4**

5.2	Rule of exclusion criteria of analysis sets.....	23
6	Reference	24

List of abbreviations

AE	Adverse event
ATC	Anatomical Therapeutic Classification
AUC	Area Under the Curve
bid	bis in diem/twice a day
CSR	Clinical Study report
CTC	Common Toxicity Criteria
CTCAE	Common Terminology Criteria for Adverse Events
DAR	Dose administration record
DMC	Data Monitoring Committee
FAS	Full Analysis Set
eCRF	Electronic Case Report Form
IVR	Interactive Voice Response
IWR	Interactive Web Response
MedDRA	Medical Dictionary for Drug Regulatory Affairs
NCI	National Cancer Institute
o.d.	Once Daily
OS	Overall Survival
PDS	Programming datasets specifications
PFS	Progression-Free Survival
PK	Pharmacokinetics
PPS	Per-Protocol Set
PRO	Patient-reported Outcomes
qd	Quaque die / once a day
QoL	Quality of Life
RAP	Report and Analysis Process
RECIST	Response Evaluation Criteria in Solid Tumors
SAP	Statistical Analysis Plan
SOC	System Organ Class
TFLs	Tables, Figures, Listings
WHO	World Health Organization

1 Introduction

This document describes details of the analyses as outlined in section 12 of the study protocol. Results will be summarized in the clinical study report (CSR). However, since this is an open-label study with regular review of safety outcomes, selected outputs may also be generated during the course of the study.

1.1 Study design

[figure not shown]
This trial is a multicenter, open-label long-term extension (OLE) study for subjects who have successfully completed Part 2 of the PANORAMA-HF trial. Subjects will be enrolled into two different age groups (Age Group 1: 6 years and older; Age Group 2: 1 to < 6 years) in the OLE study. Age Groups 1 and 2 in the OLE have a target dose (dose level 4) of 3.1 mg/kg bid. Subjects will be up titrated to the target dose of sacubitril/valsartan, dose level 4, according to their tolerability, in 2-weeks intervals. An outline of the study design is presented in [Figure 1-1](#).

No specific sample size is required for the study. However, all patients who have completed the double-blind phase of the study PANORAMA-HF, and fulfill all inclusion/exclusion criteria, are eligible for the study.

The primary analysis will be conducted when all patients who are still ongoing (i.e., did not prematurely discontinue) have had their end of study visit (EoS).

No interim analysis is planned. However, the safety will be monitored through regular review of adverse events and related data.

Figure 1-1 Study design

w=weeks; m=months; DL=LCZ696 dose level

* ≥36 hour of ACEI or double-blind study medication-free washout before starting OLE study medication at Visit 501

** The starting dose at V501 can vary according to prior dose of ACEI/ARBs or PANORAMA-HF study drug

1.2 Study objectives and endpoints

This study has only primary objective as described in [Table 1-1](#).

Table 1-1 Objectives and related endpoints

Primary Objective	Endpoint(s) for primary objective

To further evaluate long-term safety and tolerability of sacubitril/valsartan in eligible PANORAMA-HF subjects receiving open-label sacubitril/valsartan	
AEs, SAEs, laboratory values, vital signs, and duration of drug exposure

2 Statistical methods

2.1 Data analysis general information

Unless otherwise specified, the data will be analyzed according to the study protocol using SAS 9.4 or higher and R 3.4.3 or higher, by Novartis personnel.

In general, continuous variables will be summarized using number of observations, mean, standard deviation, median, quartiles, minimum and maximum. Categorical variables will be summarized using frequencies and percentages. Unless otherwise specified, the by age group summaries will include: summary for the two age groups (6 years and older, 1 year to < 6 years) and summary for the entire analysis set.

Study completion is defined as having reached the end of study visit (December 2023 from Protocol Amendment V.01 and later versions or December 2022 for Protocol V.00) while on treatment, or having completed 12 months of study while being on treatment and being transitioned to commercial Entresto.

Data from all study centers will be combined.

2.1.1 General definitions

Study treatment is sacubitril/valsartan.

The date of first administration of study treatment is the day of the first dose of sacubitril/valsartan.

The date of last administration of study treatment is the day of the last non-zero dose of sacubitril/valsartan.

Study day is defined as actual date – date of first administration of study treatment + 1.

Baseline is defined as last non-missing value before starting treatment, where for the same parameter, central laboratory result takes precedence over local laboratory result; in general values are obtained at the baseline visit (501), with the exception of urinalysis and complete laboratory, which are obtained at the screening visit (500). In case these two visits happened on the same day, results from the central laboratory will be considered as baseline values. Note that per protocol, in the case that visit 500 and, if applicable visit 501, is scheduled within 14

days of the PANORAMA-HF End of Study visit (Visit 416), the assessment results from PANORAMA-HF End of Study visit can be used as screening/baseline.

The **study period** starts with the date of screening visit (500) and ends with the date of end-of-study (EOS) or premature study discontinuation (PSD) visit (599).

Treatment period starts with the date when the first dose of study treatment is given (visit 501, unless no dose is given at that visit) and ends with the date of treatment disposition. In the case that no EOS visit was undertaken (e.g., because the patient died or withdrew from the study without such a visit), the treatment period ends with the death/withdrawal date or the last dose taken as reported in the DAR page. Subjects who permanently discontinued study drug should be scheduled for the discontinuation study Visit 599. Note that after a consecutive 3-month interruption of study treatment, subject should be discontinued from the study and should be seen at the site for Visit 599.

2.2 Analysis sets

The following analysis sets will be used:

- Screened set (SCR): All patients who signed the informed consent for the extension open-label study.
- Safety Set (SAF): All SCR patients who received at least one dose of open-label study treatment during the extension open-label study.

2.2.1 Subgroup of interest

The patients satisfying the criterion of being within the age range of 2-9 years at each 12-month visit (e.g., patients aged 8 years at baseline will only be included in the analysis of height at their first 12-month visit) starting from baseline until EOS will be investigated, other than the age groups specified in [Section 2.1](#).

2.3 Patient disposition, demographics and other baseline characteristics

2.3.1 Patient disposition

The number and percentage of patients who completed the screening phase will be provided by age group. In addition, the primary reason for not completing the screening phase will be summarized by age group using the numbers and percentages of patients not qualifying for such reasons and criteria leading to exclusion from the analysis will be provided by age group. For patients who are screen failures and re-screened, the rescreening visit will be used. These summaries will be performed for the SCR.

The number and percentage of patients who complete the treatment, who discontinue from the treatment and the primary reasons for discontinuation will be summarized by age group. In addition, the number and percentage of patients with protocol deviations will be provided by age group. These summaries will be performed based on the SAF.

2.3.2 Demographics and baseline characteristics

Summary statistics will be provided by age group and for overall for demographics and baseline characteristics, including age, age group (only for overall), sex, race, ethnicity, weight, height, head circumference (for subjects \leq 3 years old), BMI, vital signs, age adjusted percentile for weight, height and body mass index (BMI = weight (kg) / height² (m²)), z-score for height .

Continuous variables will be summarized using n, mean, standard deviation, median, minimum, the first quartile (Q1), the third quartile (Q3), and maximum. Categorical variables will be summarized using frequencies and percentages. The SAF will be used for the above analyses.

2.3.3 Medical history

Any condition entered on the relevant medical history/current medical conditions CRF will be coded using the MedDRA dictionary. Medical history includes heart failure history and other medical history in this study, which are collected at screening (Visit 500). The number and percentage of patients with each medical condition will be provided by age group and for overall, by system organ class (SOC), high level group term (HLGT) and preferred term (PT).

The SAF will be used for the above analyses.

2.4 Treatments (study treatment, rescue medication, concomitant therapies, compliance)

2.4.1 Study treatment / compliance

All analyses in this section will use the SAF.

The study drug administration is recorded on the CRF page: “Dosage Administration Record” using start date-time, end date-time and dispensing level of the study drug. Each pair of start date and end date will be considered as a dosing interval.

For each patient, the dosing intervals will be sorted according to the start date and the end date of the dose. For subject with gaps and/or overlaps among dosing interval (e.g., when the patient takes the previous dispensing level in the morning and starts a different dispensing level in the evening, the end date of a dosing interval is the same as the start date of the next dosing interval), a conventional data imputation algorithm will be applied to the start date and end date. The detailed algorithm will be provided in the study programming datasets specifications (PDS).

For patients who permanently discontinue study treatment, there should be a dosing interval with its start date equal to the date of the permanent discontinuation of the study drug, its end date equal to the study discontinuation date, and its dispensing level equal to “No treatment”.

Patients who complete the treatment are defined as receiving study treatment as reported in the DAR page until the day of EoS or the date marked as “treatment complete” in the disposition page.

The specific doses based on the dispensing dose levels are defined in [Table 2-1](#) for both the pediatric and adult formulation. If the dispensing level is no treatment, the dose level is defined as 0.

For a dosing interval with a pediatric dose level, the daily dose (mg/day) during the interval is defined as the product of the weight based daily dose (mg /kg/day) during the interval and the weight during the interval, where the weight based daily dose (mg /kg/day) during the interval is defined in [Table 2-1](#) and [Table 2-2](#) and the weight during the interval is defined as the weight from the last non-missing assessment (scheduled or unscheduled) prior to or equal to the start dose time of the study drug of the interval.

Table 2-1 Study drug dose levels and doses for sacubitril/valsartan

Age groups 1 and 2 *		
Dispensing dose levels for pediatric formulation		Weight based daily dose
Dose level 1	0.8 mg/kg bid.	1.6 mg/kg/day
Dose level 2	1.6 mg/kg bid.	3.2 mg/kg/day
Dose level 3	2.3 mg/kg bid.	4.6 mg/kg/day
Dose level 4	3.1 mg/kg bid.	6.2 mg/kg/day
Dispensing dose levels for adult formulation		Weight based daily dose
Dose level 1	50 mg bid.	1.6 mg/kg/day
Dose level 2	100 mg bid.	3.2 mg/kg/day
Dose level 3	150 mg bid.	4.6 mg/kg/day
Dose level 4	200 mg bid.	6.2 mg/kg/day

*Note: sacubitril/valsartan target dose (dose level 4) for age groups 1 and 2 is 3.1 mg/kg bid.

Table 2-2 Tablet use for sacubitril/valsartan (43 to < 57 kg patients)

Study drug	Pediatric dose level	Patient weight (kg)	Pediatric dose	Tablet dose
LCZ696	Dose level 4	43 to < 57 kg	>= 133 to < 177 mg	150 mg
	Dose level 3	43 – 54 kg	>= 98 to <125 mg	100 mg
	Dose level 3	>54 to <57 kg	>= 125 to < 131 mg	150 mg

Dispensing level (dose level) and daily dose at each visit

For a given visit, the visit associated dosing interval is defined as the dosing interval with its start date prior to or equal to the date of visit AND its end date later than or equal to the date of visit; the dose level and weight based daily dose (mg/ kg/day) at the visit are defined as the dose level and weight based daily dose (mg/kg/day) for the visit associated dosing interval. In the case that, the visit date is equal to the end date of an earlier dosing interval as well as the start date of a later dosing interval, the later dosing interval will be taken as the visit associated dosing interval.

The dose level will be summarized by visit, for overall and for each age group, using the number and percentage of patients on each level; and further be summarized using number of observations, mean, standard deviation, median, minimum, Q1, Q3, and maximum; the weight based daily dose (mg /kg/day) will be summarized by visit, for overall and for each age group, using number of observations, mean, standard deviation, median, minimum, Q1, Q3, and maximum.

The summary will include all scheduled visits in the study or until treatment discontinuation date.

Duration of treatment exposure

Duration of exposure to treatment regardless of temporary interruptions is defined as: date of last dose of study treatment – date of first dose of study treatment + 1.

Conversion for treatment exposure durations is as follows:

- 1 week = 7 days
- 1 month = 30.4375 days
- 1 year = 365.25 days

Total (sum of patient-years) and per-patient duration of exposure to the study treatment will be summarized for each age group and for overall in years, using mean, standard deviation, median, Q1, minimum, Q3 and maximum.

The duration (day) of treatment exposure excluding study drug interruptions is defined as the sum of the duration (day) on dose level 1 to 4 during the study without counting any days that patients are not taking the treatment.

The analyses specified in the Section “Dispensing level (dose level) and daily dose at each visit” will be used here. In addition, the duration of study drug exposure with and without study drug interruptions, respectively, will be categorized into:

- < 6 months
- 6 months to < 1 year
- 1 to < 2 years
- 2 to < 3 years
- 3 to < 4 years
- >=4 years.

The number and percentage of patients within each category by age group and overall will be tabulated.

Duration on each dose level

For a given dose level, the duration (day) on this dose level is defined as the number of days on this dose level during the period from the date of the first dose of the study drug to the date of the last dose of the study drug. In the case that the end date of an earlier dosing interval is the same as the start date of a later dosing interval, the day will be counted as 0.5 day on both the earlier dose level and the later dose level. In the case that the date of permanent discontinuation of the study drug is the same as the date of the last dose of the study drug, the day will be counted as 0.5 day on the dose level of the last dose but not counted on dose level 0.

The median and interquartile range will be presented for duration on each dose level. The number of patients who have ever been on a specific dose level will be reported.

Time to permanent discontinuation of the study drug

The time (day) to permanent discontinuation of the study drug during the study (excluding death) will be summarized for each age group and overall by duration categories (refer to the Section “Duration of study drug exposure” for specific categories) using the Kaplan-Meier curves, considering time-to-death, completion of the study and switch to commercial entresto as independent censoring.

Mean weight based daily dose and mean dose level

For each patient, the mean weight based daily dose (mg/kg/day) during the study is defined as the weighted mean of the weight based daily dose (mg/kg/day) among dose level 0 to 4 using the duration (day) on each dose level as the weight, i.e.

$$\frac{\sum_{k=0}^4 \text{Weight Based Daily Dose (mg/kg/day)} \text{ for Dose Level } k \times \text{Duration (day) on Dose Level } k}{\sum_{k=0}^4 \text{Duration (day) on Dose Level } k}$$

the mean dose level is defined as the weighted mean of the dose level among dose level 0 to 4 using the duration (day) on each dose level as the weight, i.e.,

$$\frac{\sum_{k=0}^4 k \times \text{Duration (day) on Dose Level } k}{\sum_{k=0}^4 \text{Duration (day) on Dose Level } k}$$

The mean weight based daily dose (mg /kg/day) and the mean dose level during the study will be summarized for each age group and overall, using number of observations, mean, standard deviation, median, minimum, Q1, Q3, and maximum.

Dose down titration

A down-titration dosing interval is defined as a dosing interval whose dose level is changed to a lower dose level from its previous dosing interval.

The dose down titration during the study will be summarized by each age group and overall, using the numbers and percentages of patients with at least one down-titration dosing interval during the study.

Dose interruption

A dose-interruption dosing interval is defined as a dosing interval with “NO TREATMENT”.

The numbers and percentages of patients with at least one dose-interruption greater than 24-hour dosing interval during the study will be provided by age group and the overall.

The numbers and percentages of patients having at least one dose-interruption dosing interval with duration (day) of dose-interruption larger than 14 days will be provided by each age group and overall.

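### SAP Table 2-1 gives fixed-mg adult tablets the pediatric mg/kg/day values at every body weight, so the mg/kg/day summaries do not show the dose dispensed to tablet users

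*SAP*

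**What the plan says.** SAP section 2.4.1 makes Table 2-1 the definition of dose "for both the pediatric and adult formulation". The pediatric rows list 0.8, 1.6, 2.3 and 3.1 mg/kg bid with daily values of 1.6, 3.2, 4.6 and 6.2 mg/kg/day. The rows under "Dispensing dose levels for adult formulation" list 50, 100, 150 and 200 mg bid with the same four daily values and no weight condition.

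Measured weight enters in one place. "For a dosing interval with a pediatric dose level", mg/day is the mg/kg/day value multiplied by weight, "where the weight based daily dose (mg /kg/day) during the interval is defined in" Tables 2-1 and 2-2. The weight is "the weight from the last non-missing assessment (scheduled or unscheduled) prior to or equal to the start dose time of the study drug". No rule divides a tablet dose by weight.

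Table 2-2 covers tablet users of 43 to <57 kg at pediatric levels 3 and 4. It gives a pediatric dose range and a tablet dose, both in mg. At level 4 the pediatric dose is ">= 133 to < 177 mg" while the tablet dose is 150 mg throughout.

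Two outputs use mg/kg/day: a by-visit summary, and a per-patient mean that weights one value per dose level (0 to 4) by the days spent on that level.

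**The concern.** A fixed number of milligrams equals a given mg/kg/day at only one body weight. Carrying the pediatric values into the tablet rows turns mg/kg/day into a code for dose level. The outputs will nevertheless be headed mg/kg/day and summarized with mean, SD, quartiles and range, as if they measured dose per kilogram.

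The participants are growing children followed for up to about 4.5 years (Protocol section 3). A patient on an unchanged tablet dose receives less per kilogram as weight rises, but the planned table would show a flat line. A reader using it to relate long-term safety to dose received would be misled about tablet users, and nothing in section 2.4.1 warns of this.

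**Working it through.** **Inputs.** Tablet and pediatric doses and their mg/kg/day values: SAP Table 2-1. Weight bands and tablet doses: SAP Table 2-2.

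**Reproducing the plan's figures.** Pediatric rows: 2 × 0.8, 1.6, 2.3 and 3.1 = 1.6, 3.2, 4.6 and 6.2 mg/kg/day, which is exact. The pediatric dose column of Table 2-2 also reproduces per administration: 43 × 3.1 = 133.3 and 57 × 3.1 = 176.7 mg. The tablet column is therefore read as a bid dose too.

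**Adult rows.** Actual mg/kg/day = 2 × tablet mg / weight, so the stated value is exact only at weight = 2 × tablet mg / stated value:

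- Level 1: 100 / 1.6 = 62.5 kg
- Level 2: 200 / 3.2 = 62.5 kg
- Level 3: 300 / 4.6 = 65.2 kg
- Level 4: 400 / 6.2 = 64.5 kg

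**Table 2-2 rows coded by pediatric level.** Error = reported value / (2 × tablet mg / weight) − 1.

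| Row | Weight (kg) | Actual | Reported | Error |
|---|---|---|---|---|
| Level 4, 150 mg | 43 | 300/43 = 6.98 | 6.2 | -11.1% |
| Level 4, 150 mg | approaching 57 | 300/57 = 5.26 | 6.2 | +17.8% |
| Level 3, 100 mg | 43 | 200/43 = 4.65 | 4.6 | -1.1% |
| Level 3, 100 mg | 54 | 200/54 = 3.70 | 4.6 | +24.2% |
| Level 3, 150 mg | just above 54 | 300/54 = 5.56 | 4.6 | -17.2% |
| Level 3, 150 mg | approaching 57 | 300/57 = 5.26 | 4.6 | -12.6% |

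The reported value is exact at 300/6.2 = 48.4 kg in the first row and at 200/4.6 = 43.5 kg in the second. The third row would need 300/4.6 = 65.2 kg, which lies outside its own band.

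**Same tablets, same weight, two values.** At 55 kg, 150 mg bid is 300/55 = 5.45 mg/kg/day. It is reported as 4.6 (-16%) at level 3 or 6.2 (+14%) at level 4.

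**If the same tablets were coded by the adult row.** 150 mg reported as 4.6 is -34% at 43 kg (4.6/6.98 − 1) and -13% approaching 57 kg. 100 mg reported as 3.2 is -31% at 43 kg (3.2/4.65 − 1) and -14% at 54 kg (3.2/3.70 − 1). This coding does not cure the problem.

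**Adult rows above the Table 2-2 band.** The SAP states no weight range. Over an assumed 57 to 80 kg:

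- Levels 1 and 2: -9% to +28%; for level 1, 1.6/(100/57) − 1 and 1.6/(100/80) − 1
- Level 3: -13% to +23%; 4.6/(300/57) − 1 and 4.6/(300/80) − 1
- Level 4: -12% to +24%; 6.2/(400/57) − 1 and 6.2/(400/80) − 1

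**Growth, as an illustration.** On a constant 200 mg bid, a rise from 57 to 70 kg takes the actual value from 400/57 = 7.02 to 400/70 = 5.71 mg/kg/day. The plan reports 6.2 at both weights.

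**The mg/day rule.** Applied to level 4 it gives 6.2 × 43 = 266.6 and 6.2 × 56.9 = 352.8 mg/day, against 2 × 150 = 300 mg/day in tablets. No mg/day table is specified, so this shows the inconsistency but does not reach an output.

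**The case against.** The strongest reply is that this is a convention, not an error. The dosing record is described as "using start date-time, end date-time and dispensing level of the study drug", the mean formula takes one value per level, and Protocol Table 3-2 already pairs tablets with mg/kg doses under the same level numbers. On that reading the variable is level-assigned for everyone. Table 2-2 then works as a lookup: weight band and tablet give a pediatric level, and Table 2-1 supplies its value.

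That describes how the number would be produced, but it does not make it a dose per kilogram. Section 2.4.1 never calls it nominal, and it uses measured weight for mg/day, so a reader would expect weight-specific values. Reading Table 2-2 through its pediatric level yields the same constants that fail above.

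Several points do stand:

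- The documents give neither the number of tablet users nor their weights, so the effect on the summary tables cannot be estimated. Errors run in both directions and are small near 62.5 to 65 kg.
- The 57 to 80 kg range is an assumption, and the adult-row figures for 43 to <57 kg rest on a coding that Table 2-2's pediatric-level column points away from.
- mg/kg/day is not a listed primary endpoint.
- Actual values for tablets beside nominal values for pediatric formulations make a mixed summary. Interval-start weight can also go stale: a 20% gain within an interval would overstate mg/kg/day by 20%.

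**Conclusion.** The point holds. For tablet users, Table 2-1 assigns a level constant and the SAP summarizes it as mg/kg/day. Within the SAP's own 43 to <57 kg band, coded by pediatric level, the misstatement runs from -17% to +24% with no outside weight assumption. Above that band its size depends on weights the documents do not give.

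The consequence is limited to the descriptive by-visit and per-patient mean mg/kg/day summaries. Dose-level counts, mean dose level, down-titration counts, duration of exposure and adverse event rates do not use mg/kg/day. It should be corrected, but it does not threaten the main safety results. The finding concerns how the dispensed dose is reported, not which dose is right.

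**What to change.** For all tablet intervals, including those under Table 2-2, define mg/kg/day as 2 × dispensed tablet mg / interval weight, using the existing weight rule in section 2.4.1. Then:

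- Name the source variable for tablet mg (the dosing record or IRT). The SAP describes the dosing record by dispensing level only, so this cannot be left implicit.
- Rewrite the per-patient mean as a duration-weighted mean over dosing intervals, keeping no-treatment intervals at 0 and the half-day rule.
- Label pediatric-formulation values, and any Table 2-1 constant that is kept, as nominal. Footnote that the summary combines actual tablet values with nominal pediatric-formulation values.
- Correct the reference to Table 2-2 and state which dose level and mg/kg/day apply to its intervals, without altering any dose.

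If the sponsor prefers to keep the constants, the minimum is a nominal label on every mg/kg/day output.

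The cost is SAP wording, one interval-level derivation and a revised formula. The inputs are already planned: dosages on the dosing record (Protocol 6.7.2), dispensing and dosage changes in IRT (Protocol 11.2), and weight at every site visit (Protocol Table 8-2). The drawbacks are some extra programming, a summary that mixes actual and nominal values, and interval-start weights that may be out of date in long intervals. The label-only option costs one footnote but still leaves tablet users with level constants.
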